9.1.4. Posttreatment Phase (Follow-Up)

For all cohorts, subjects will be evaluated for a total of approximately 28 (± 3) days post randomization

Both Cohort 1 subjects after discharge and Cohort 2 subjects will be required to return to the site for follow-up assessments as an outpatient on Day 14 and Day 21, as indicated in the [TIME AND](#)

EVENTS SCHEDULE. These scheduled study visits if feasible for the study site and if allowed per local regulations, can also be done as home visits. On Day 28 (± 3), subject's parent(s)/caregiver(s) will be contacted by the site staff for a telephone follow-up visit. In case a subject is experiencing (an) ongoing AE(s) or has clinically significant laboratory or ECG abnormalities at the time of the Day 21 Follow-Up Visit, parent(s)/caregiver(s) might be requested, at the discretion of the investigator, to have a Safety Follow-up Visit for the subject at the site (preferred option) or, if feasible for the study site and if allowed per local regulations, at home on Day 28 (± 3). Only clinically relevant assessments will be performed during this visit, as applicable.

During the follow-up phase, for both cohorts, the parent(s)/caregiver(s) will complete the parent(s)/caregiver(s) PRESORS as of Day 9 through Day 14 twice a day (morning and evening; see **TIME AND EVENTS SCHEDULE**). From Day 15 through Day 21, the parent(s)/caregiver(s) will complete the parent(s)/caregiver(s) PRESORS once daily, in the evening, with the final parent(s)/caregiver(s) PRESORS assessment being scheduled at the Day-21 on-site visit (see **TIME AND EVENTS SCHEDULE**). Investigational staff will review daily the completion of the parent(s)/caregiver(s) PRESORS once data is transmitted to the database from the electronic device and will contact the parent(s)/caregiver(s) in case of incompliance. Investigational staff will also instruct parent(s)/caregiver(s) on the continuation of the collection of nasal swabs, as applicable (see Section 3.1).

For all cohorts, in case subjects prematurely discontinue study drug treatment for any reason (except withdrawal of consent), the parent(s)/caregiver(s) will be asked to continue with the subject's remaining study visits and assessment schedule, or, at a minimum, to return with the subject to the site for a Withdrawal and a Safety Follow-up Visit. At the Withdrawal and Safety Follow-up Visits, the same assessments as on the Day 8 and Day 21 visits, respectively, will be performed. In case the subject's legally acceptable representative(s) withdraw consent during the treatment or follow-up phase, an optional Withdrawal and Safety Follow-up Visit will be offered. At these optional Withdrawal and Safety Follow-up Visits, the same assessments as on the Day 8 and Day 21 visits, respectively, will be performed. Assessments will be performed as indicated in the **TIME AND EVENTS SCHEDULE**.

9.2. Efficacy Evaluations

9.2.1. Antiviral Activity

As an evaluation of antiviral activity, the RSV viral load in nasal mid-turbinate swab samples will be measured at the central lab using a qRT-PCR assay. Mid-turbinate swab specimens for the determination of RSV viral load will be collected at several timepoints during the study as indicated in the **TIME AND EVENTS SCHEDULE**. Date and time of sampling will be collected. Mid-turbinate swabs should be collected from the same nostril throughout the study (unless precluded due to bleeding). The nostril that was sampled will be documented by the site staff (nasal swabs taken on-site) or by parent(s)/caregiver(s) (nasal swabs taken at home).

On Day 1, in both cohorts, the mid-turbinate nasal swab should be collected as close as possible and prior to the first administration of study drug. The next swabs should be collected from the

same nostril preferably at approximately the same time as the predose swab taken on Day 1 and preferably prior to dose administration.

- Cohort 1:

During hospitalization: Swabs will continue to be collected each day during hospitalization through Day 13 or until discharge (whichever comes first).

Discharged subjects: After discharge, swabs will be collected daily through Day 8 in all subjects. As of Day 8, in subjects who were symptomatic based on clinician PRESORS at Day 8, daily swabs will be collected through Day 13 or until the subject becomes asymptomatic based on the parent(s)/caregiver(s) PRESORS, as evaluated by the investigational staff (whichever comes first).

- Cohort 2: Swabs will be collected daily through Day 8 in all subjects. As of Day 8, in subjects who were symptomatic based on clinician PRESORS at Day 8, daily swabs will be collected through Day 13 or until the subject becomes asymptomatic based on the parent(s)/caregiver(s) PRESORS, as evaluated by the investigational staff (whichever comes first).

On Day 14 and Day 21, a swab will be collected during the scheduled visit for all subjects.

The investigational staff will collect mid-turbinate swabs during the scheduled (on-site) visit (Cohort 1 after discharge and Cohort 2) or during hospitalization (Cohort 1). When no on-site visit is scheduled per the [TIME AND EVENTS SCHEDULE](#), it may be agreed between the study site and parent(s)/caregiver(s) to perform a visit for nasal sampling purposes only, or send an HCP to the subject's home for collection of the nasal swab sample. In case collection by an HCP is not possible, the investigator/study site personnel will train the parent(s)/caregiver(s) to collect the mid-turbinate nasal swab. The training to collect and document nasal swabs will be done at screening, and repeated before discharge if needed for Cohort 1.

The collection of these nasal swab and date and time of sampling should be recorded for all subjects in the eCRF or in the nasal swab log on the electronic device (see [Attachment 7](#)), as described in the eCRF completion guidelines and the completion guides for the electronic device, which will be provided to the investigator (see Section [15](#)).

All parent(s)/caregiver(s), after being properly trained, will be provided with appropriate mid-turbinate nasal swabs and Universal Transport Medium (same supplies as those used to collect nasal samples at the sites) to collect mid-turbinate nasal swabs. All swabs collected at home by the parent(s)/caregiver(s) should be stored immediately between 2°C and 8°C (in the refrigerator) and brought to the site at the next scheduled visit.

Additional information about the collection, handling, and shipment of biological samples can be found in the laboratory manual.

RSV RNA viral load can also be measured by a qRT-PCR assay in nasopharyngeal and/or tracheal aspirate samples in a subgroup of hospitalized subjects (Cohort 1 only) in which these samples are obtained as part of their SOC, which may be used to assess virologic parameters.

The RSV infectious virus load as measured by quantitative culture of RSV (plaque assay), if feasible, on selected nasal swab samples, may be used to assess virologic parameters.

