2.1.2. Endpoints

Primary Endpoint

The primary efficacy endpoint is the RSV viral load area under the curve (AUC) from immediately prior to first dose of study drug through Day 5 derived from the RSV viral load as measured by a qRT-PCR assay in nasal swabs.

Secondary Endpoints

The secondary endpoints are:

- virologic parameters derived from the RSV viral load as measured by a qRT-PCR assay in nasal swabs including:
 - RSV viral load and change from baseline over time
 - RSV viral load AUC from immediately prior to first dose of study drug (baseline) through Day 3, Day 8, and Day 14
 - time to undetectable RSV viral load
 - proportion of subjects with undetectable RSV viral load at each timepoint throughout the study
- clinical course related endpoints:
 - in hospitalized subjects and outpatients:
 - following endpoints will be based on the Pediatric RSV Electronic Severity and Outcome Rating System (PRESORS) assessed throughout the study by parent(s)/caregiver(s) (parent[s]/caregiver[s] PRESORS) and by the investigator (clinician PRESORS) during scheduled visits:
 - duration and severity of signs and symptoms of RSV disease
 - change from baseline in parent(s)/caregiver(s) PRESORS scores (worsening or improvement)
 - change from baseline in clinician PRESORS scores (worsening or improvement)

- ◆ time to resolution (ie, to none or mild) of RSV symptoms
- ◆ time to improvement based on general questions on overall health
- ◆ proportion of subjects with improvement or worsening of RSV disease based on general questions on overall health
- ◆ time to return to pre-RSV health as rated by the parent(s)/caregiver(s)
- respiratory rate, heart rate, body temperature, and peripheral capillary oxygen saturation (SpO₂) over time as measured by the investigator during scheduled visits.

Note: If the subject is enrolled in the substudy of Study 53718678RSV2002 (see Section 3.1), the same parameters as assessed by the biosensor will be recorded from the standard-of-care monitoring/assessments as part of the substudy assessments (refer to the substudy Clinical Protocol for detailed information).

- body temperature as measured by the parent(s)/caregiver(s) and recorded in the temperature log ([Attachment 8](#)) on the electronic device
- need for (re)hospitalization during treatment and follow-up

in hospitalized subjects only:

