11.4.1.2. Secondary Endpoints

The other antiviral endpoints will be analyzed graphically and descriptively as described in the SAP. For continuous variables, descriptive statistics (n, mean, SD, median, minimum, and maximum) will be calculated. For categorical variables, frequency tables will be presented. Kaplan-Meier Curves will be produced to graphically describe the time to event data.

Differences between treatment groups in viral load will be derived from the same model as for the primary endpoint using appropriate contrasts deriving least square mean differences, including the 95% 2-sided CIs. Other covariates as well as interaction effects might also be investigated.

The time to undetectable RSV viral load will be analyzed using Kaplan-Meier plots and will be modeled using an accelerated failure time model, adjusted for covariates, such as strata and baseline viral load, to estimate differences between treatment groups. A generalized MCP-Mod approach will be used to test for existence of dose-response, if applicable. For the MCP-Mod approach, doses of the different age groups will be pooled and transformed to the total daily dose of the oldest age group: low dose (3 mg/kg), high dose (9 mg/kg), and placebo (0 mg/kg) and these will be used for the "treatment groups" in the analysis.

More details regarding the analysis of these data will be described in the SAP.

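### Day 9–13 swabbing of non-hospitalized children depends on symptoms, so undetectable proportions on those days describe a selected subset, and time to undetectable is interval-censored with a symptom-dependent width that the protocol does not address

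*Protocol*

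**What the plan says.** Sampling (Protocol Section 9.2.1, repeated in the Time and Events Schedule footnotes):

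- Through Day 8 everyone is sampled daily: "Cohort 2: Swabs will be collected daily through Day 8 in all subjects", with the same rule for discharged Cohort 1 children.
- On Days 9–13, for Cohort 2 and discharged Cohort 1: "in subjects who were symptomatic based on clinician PRESORS at Day 8, daily swabs will be collected through Day 13". This extra swabbing ends sooner if the child's symptoms clear first. The scale that starts it is the clinician's; the scale that ends it is the parent's or caregiver's.
- Cohort 1 children still in hospital are swabbed every day until discharge or Day 13, whatever their symptoms.
- Then: "On Day 14 and Day 21, a swab will be collected during the scheduled visit for all subjects".

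Endpoints and analysis that span Days 9–13:

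- Section 2.1.2: "proportion of subjects with undetectable RSV viral load at each timepoint throughout the study".
- Section 2.1.2: "RSV viral load AUC from immediately prior to first dose of study drug (baseline) through Day 3, Day 8, and Day 14".
- Section 11.4.1.2: "The time to undetectable RSV viral load will be analyzed using Kaplan-Meier plots and will be modeled using an accelerated failure time model". The other antiviral endpoints are to be shown graphically and descriptively, and further detail is left to the SAP.

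Section 3.2 expects that treatment may make RSV signs and symptoms shorter and milder.

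**The concern.** Who is swabbed on Days 9–13 is decided after randomization by something the drug is meant to change. Two consequences follow.

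1. **By-timepoint proportions.** A Day 11 proportion among swabbed children refers to those still symptomatic (plus any still in hospital), not to the randomized arms. If slow symptom resolution goes with slow clearance, the subset is enriched for slow clearers. If treatment also shortens symptoms, the enrichment is stronger in the active arms.
2. **Time to undetectable.** A child who clears on Day 9 is recorded at Day 9 if still symptomatic at Day 8 (clearance known to lie between Days 8 and 9), but at Day 14 if asymptomatic at Day 8 (between Days 8 and 14). The censoring interval is 1 day wide in one case and 6 in the other.

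At stake is the reading of secondary virology in a study meant to guide Phase 3 dose and endpoint selection.

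**Working it through.** The plan gives no figure to reproduce, so the check simulates the Section 9.2.1 schedule for non-hospitalized children. **Every numerical input below is an assumption except the visit days and the 50 per arm, which is the Cohort 2 target in Section 3.1.**

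**Model.** Time to undetectable V = m_V·exp(σ_V·Z1); time to asymptomatic S = m_S·exp(σ_S·Z2); corr(Z1, Z2) = ρ. One symptom time stands for both PRESORS versions. On day d (9–13) a child is swabbed if S > 8 and S > d − 1. The true proportion is P(V ≤ d); the observed one is P(V ≤ d | swabbed).

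**Main scenario, no virologic effect.** m_V = 10 days in both arms, σ_V = 0.4; m_S = 8.5 days (control) and 6.5 days (active), σ_S = 0.5; ρ = 0.5; 100,000 per arm.

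Closed-form checks:

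- Symptomatic at Day 8, control: Φ(ln(8.5/8)/0.5) = Φ(0.12) = 55%. Active: Φ(ln(6.5/8)/0.5) = Φ(−0.42) = 34%.
- True Day 11 proportion: Φ(ln(11/10)/0.4) = Φ(0.24) = 59%.

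| Day | Swabbed, control / active | Observed undetectable, control vs active | True, both arms | Observed difference |
|---|---|---|---|---|
| 9 | 55% / 34% | 25% vs 19% | 40% | −6 points |
| 11 | 37% / 19% | 39% vs 30% | 59% | −9 points |
| 13 | 24% / 11% | 51% vs 41% | 74% | −10 points |
| 14 | 100% / 100% | 80% vs 80% | 80% | 0 |

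Monte Carlo standard error of the Day 11 difference: √(0.39·0.61/37,000 + 0.30·0.70/19,000) ≈ 0.4 points.

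**Varying the assumptions (proportions).**

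- Equal symptom courses, no virologic effect: Day 11 is 39% in both arms against a true 59%; difference about 0.
- ρ = 0, symptoms 8.5 vs 6.5 days: no distortion.
- Symptoms 20% shorter, no virologic effect: about −8 to −11 points at ρ = 0.5, −4 to −6 at ρ = 0.3, 0 at ρ = 0. For example, with clearance median 9 days (log-SD 0.35), symptoms 8 vs 6.4 days (log-SD 0.40) and ρ = 0.5, Day 10 shows 42% vs 33% where 62% have truly cleared in both arms.
- True virologic effect (median 10 vs 8.5 days), symptoms 8.5 vs 6.5 days: Day 9 difference 8 points observed, 16 true; Day 13, 9 observed, 11 true.
- Same virologic effect, equal symptom courses: Day 9, 16 observed and 16 true; Day 13, 17 observed, 11 true.

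**Time to undetectable (lognormal AFT time ratio, ρ = 0.5).**

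| True ratio | Symptom medians | Daily swabs for all, exact dates | Actual schedule, exact dates | Actual schedule, interval-censored |
|---|---|---|---|---|
| 1.00 | 8.5 vs 6.5 | 1.001 | 1.028 | 1.000 |
| 0.85 | 8.5 vs 6.5 | 0.843 | 0.854 | 0.847 |
| 0.85 | 8.5 vs 8.5 | 0.846 | 0.835 | 0.850 |

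The control median of the recorded first undetectable day moves from 10–11 under daily swabbing to 14 under the actual schedule.

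Power at 50 per arm and time ratio 0.85 (clearance median 9 days, control symptom median 8 days, symptoms 20% shorter on active):

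- Log-SDs 0.35 and 0.40: 63% with daily swabs, 52% with recorded dates as exact, 63% interval-censored.
- Log-SDs 0.4 and 0.5: 51%, 44% and 49%.

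**The case against.** The strongest case against is that this is ordinary SAP detail. Section 11.4.1.2 names Kaplan-Meier plots and an AFT model and defers the rest. An AFT model accepts interval-censored data, and the SAP is not at hand. A reader might infer that the protocol treats sampling as equal and recorded dates as exact. It says neither, and that inference should not be made.

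Other points also stand:

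- Children still in hospital are swabbed daily, so the selection does not apply to them in the same way. Their daily swabbing does end at discharge, whose timing is itself an efficacy endpoint.
- The proportions are descriptive secondary endpoints. No test of them is specified, and Section 2.1.2 does not state a denominator.
- Between-arm distortion with no virologic effect needs two conditions together: symptoms shifted by treatment, and symptoms correlated with clearance.
- Least-squares means and the AUC come from a likelihood-based repeated-measures model, which partly absorbs the missing days through the viral loads that were observed. Its listed terms (Section 11.4.1.1) do not include symptom status.

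What the objection does not remove is that the sampling rule and the endpoint wording are both protocol content and do not fit together. A Day 9–13 proportion for the randomized arms cannot be tabulated from swabs that were never scheduled. The two conditions are not far-fetched here: the first is the trial's own hope (Section 3.2), and the Introduction cites studies that link viral load closely to symptom severity, with one exception.

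**Conclusion.** The point holds for secondary virology in Cohort 2 and discharged Cohort 1. Day 9–13 undetectable proportions belong to a symptom-selected subset. They understate clearance when symptoms and clearance are correlated. When treatment also shortens symptoms, the between-arm difference is distorted by 0 to about −11 points with no virologic effect, over correlations of 0 to 0.5. These sizes rest wholly on assumed clearance and symptom distributions.

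For time to undetectable, the time ratio moves by only 0.01 to 0.03 in the scenarios run, and power falls by 7 to 11 points if recorded dates are taken as exact.

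A reader might infer a steady bias against the drug. The working does not support that: with equal symptom courses and a true effect, both the exact-date ratio (0.835 for a true 0.85) and the Day 13 difference (17 points for a true 11) lean in the drug's favour. Nor is the primary analysis threatened: the endpoint ends at Day 5, when all children are swabbed daily, and Days 2–8, 14 and 21 are free of the problem. This should be fixed, but it does not put the trial's main conclusion at risk.

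**What to change.** 1. Limit between-arm comparisons of undetectable proportions to the days when all children are swabbed: Days 2–8, 14 and 21.
2. Show Days 9–13 only as descriptive data on the symptomatic or hospitalized subset, labelled as such, with the number swabbed in each arm.
3. Name an interval-censored AFT model for time to undetectable, with a Turnbull curve in place of Kaplan-Meier on recorded dates.
4. Add a sensitivity analysis of the Day 14 AUC that uses only the common visits.

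The cost is wording and standard software options; no extra swabs are needed. The downside is fewer displayed comparison timepoints.

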9.2.2. Clinical Course of RSV Infection

The study will include the following evaluations of the clinical course of RSV infection:

- Cohort 1 and Cohort 2:

clinical parameters: respiratory rate, heart rate, SpO₂, and body temperature as measured by the investigator during scheduled visits. **Note:** If the subject is enrolled in the substudy of Study 53718678RSV2002 (see Section 3.1), the same parameters as assessed by the biosensor will be recorded from the standard-of-care monitoring/assessments as part of the substudy assessments (refer to the substudy Clinical Protocol for detailed information) at the timepoints indicated in the **TIME AND EVENTS SCHEDULE**.

body temperature as measured by parent(s)/caregiver(s) and recorded in the temperature log ([Attachment 8](#)) (for Cohort 1 after discharge and Cohort 2)

evolution and severity of signs and symptoms of RSV disease (fever, cough, sputum, wheezing, difficulty breathing, nasal congestion, feeding issues) as assessed by the parent(s)/caregiver(s) (parent[s]/caregiver[s] PRESORS) and the clinician (clinician PRESORS)

the need for (re)hospitalization

the occurrence of complications, bronchiolitis, or viral pneumonia with onset after treatment initiation that are associated with RSV per investigator assessment

the need for antibiotics related to complications associated with RSV per investigator assessment

- Cohort 1 only:

time to discharge (from initial admission and from initiation of treatment)

time to clinical stability, with clinical stability evaluated by the investigator (from initial admission and from initiation of treatment)

level of and duration by level of hospital care (eg, ICU, transitional care unit, ward floor)

oxygen requirement type (eg, supplemental oxygen, noninvasive pressure ventilation, endotracheal-mechanical ventilation), and duration

hydration and feeding by IV line/nasogastric tube and duration

Note: In case antipyretics are used, body temperature should be measured immediately before or >4 hours after giving antipyretics. Parents/caregivers should be instructed accordingly.

Note: In case antitussives and mucolytics are used, the PRESORS should report the worst symptom(s) during the recall period.

Clinical outcome assessments as performed separately by the clinician (clinician PRESORS) and the parent(s)/caregiver(s) (parent[s]/caregiver[s] PRESORS, temperature log) will be captured in an electronic device. Symptoms reported in these assessments will not be reported as AEs but constitute a part of the efficacy evaluations.

An electronic device will be provided to the subject's parent(s)/caregiver(s) at the time of screening, after enrollment of the subject. The investigator/study site personnel will provide sufficient information to enable the subject's parent(s)/caregiver(s) to complete these assessments. The parent(s)/caregiver(s) PRESORS assessment should be completed once at screening, then bid (in the morning and in the evening) from Day 1 (day of first dose) to Day 14 and then once daily in the evening until the Day 21 visit. The final parent(s)/caregiver(s) PRESORS assessment has to be completed during the scheduled Day-21 on-site visit (see also [TIME AND EVENTS SCHEDULE](#)). The first parent(s)/caregiver(s) PRESORS of the bid schedule on Day 1 needs to be completed as close as feasible and prior to the first administration of study drug. The screening parent(s)/caregiver(s) PRESORS assessment will be accepted as baseline if completed within 4 hours before randomization.

During hospitalization (Cohort 1), body temperature will be measured by the investigator. On the day of discharge (Cohort 1) or at screening (Cohort 2), the initial measurement of body temperature should be performed by the investigator. If discharged (Cohort 1) or screened in the morning, only the evening assessment of the bid schedule for the measurement of body temperature should be recorded in the temperature log on the electronic device ([Attachment 8](#)).

The parent(s)/caregiver(s) PRESORS and temperature log should preferably be completed by the same person throughout the study. A second parent/caregiver who frequently provides direct care of the child can be set up as a backup reporter on the electronic device to ensure assessments are recorded if the primary parent/caregiver is unable to enter information for any reason.

Investigational staff will review daily the completion of the parent(s)/caregiver(s) PRESORS and logs once data is transmitted to the database from the device. The site will contact the parent(s)/caregiver(s) in case if parent(s)/caregiver(s) PRESORS and information collected in the logs are not uploaded according to the schedule, which might be due to issues with the electronic device or due to non-compliance. The site will monitor and help the parent(s)/caregiver(s) to be compliant. Investigational staff will also instruct parent(s)/caregiver(s) on the continuation of the collection of nasal swabs, as applicable.

